4.4 Study Period

The study will begin with administration of the first dose of HEPLISAV-B and is contingent upon ACIP and RIPC recommendation of HEPLISAV-B. The study vaccination period will occur until 25,000 patients have received at least 1 dose of HEPLISAV-B, expected to take approximately 10.5 months based on historical vaccination trends. Each patient will be followed until the earliest of disenrollment from KPSC (not due to death and allowing for a 31-day gap in membership), death from any cause, or the end of the 13-month follow-up period after the index dose given during the vaccination period.

Table 4-1:Adult Hepatitis B Vaccine Recipients: Active Member at First Dose
Date, 2015 by Target (HEPLISAV-B) and Comparator Medical
Centers

	8 Comparator	7 Target	Total
	Medical Centers	Medical Centers	
N	47,964	45,766	93,730
Age (years)			
Mean (SD)	49.1 (10.83)	49.0 (10.90)	49.1 (10.86)
Sex	n (%)	n (%)	n (%)
Female	23,229 (48.43)	22,400 (48.94)	45,629 (48.68)
Male	24,735 (51.57)	23,366 (51.06)	48,101 (51.32)
Race/Ethnicity	n (%)	n (%)	n (%)
Asian	4043 (8.43)	5810 (12.7)	9853 (10.51)
Black	4027 (8.4)	4742 (10.36)	8769 (9.36)
Multiple	242 (0.5)	190 (0.42)	432 (0.46)
Native Am/Alaskan	152 (0.32)	127 (0.28)	279 (0.3)
Others	340 (0.71)	432 (0.94)	772 (0.82)
Pacific Islander	728 (1.52)	691 (1.51)	1419 (1.51)
Unknown	1107 (2.31)	829 (1.81)	1936 (2.07)
White	14,482 (30.19)	7914 (17.29)	22,396 (23.89)
Hispanic	22,843 (47.63)	25,031 (54.69)	47,874 (51.08)
Had type 2 diabetes history prior to the first dose	n (%)	n (%)	n (%)
No	9851 (20.54)	10,094 (22.06)	19,945 (21.28)
Yes	38,113 (79.46)	35,672 (77.94)	73,785 (78.72)
Had AMI history between 01/01/2010 to first dose date	n (%)	n (%)	n (%)
No	47,359 (98.74)	45,260 (98.89)	92,619 (98.81)
Yes	605 (1.26)	506 (1.11)	1111 (1.19)
Had hospitalized AMI in 12 months after first dose date	n (%)	n (%)	n (%)
No	47,891 (99.85)	45,713 (99.88)	93,604 (99.87)
Yes	73 (0.15)	53 (0.12)	126 (0.13)

5.0 STUDY POPULATION

5.1 **Recommendations for Vaccination**

The ACIP recommends hepatitis B vaccination for adults at increased risk of hepatitis B through sexual exposure, percutaneous or mucosal exposure, and travelers to countries with high or intermediate prevalence of hepatitis B ^[2-4]. Universal vaccination is recommended in settings in which a high proportion of persons are likely to be at risk (eg, STD/HIV testing and treatment facilities, drug abuse treatment and prevention facilities, etc). Persons with diabetes mellitus are also recommended for vaccination if age 19 to 59 years, or if age 60 years or older at the discretion of the health provider.

5.2 Hepatitis B Vaccination of Adults With Diabetes

In 2014, KPSC implemented an electronic alert and reminder embedded in electronic health records prompting providers to order hepatitis B vaccine for previously unvaccinated adults with diabetes ^[25]. This resulted in a significant increase in completion of the 3-dose series among adults with diabetes, although coverage with all 3 doses remained low (<30%). In 2015, adults with diabetes comprised approximately 79% of the 93,730 KPSC members who received a dose of hepatitis B vaccine (Table 4-1).

5.3 Study Inclusion and Exclusion Criteria

5.3.1 Inclusion Criteria

- 1. Received at least one dose of hepatitis B vaccine (either HEPLISAV-B in HEPLISAV-B arm, or non-dialysis formulation hepatitis B comparator vaccine in comparator arm) at KPSC during study vaccination period.
- 2. Enrolled as a KPSC member at time of hepatitis B vaccination during the study vaccination period.
- 3. Age 18 years or older at time of hepatitis B vaccination during study vaccination period.
- 4. Received hepatitis B vaccine at KPSC family practice or internal medicine departments, or in urgent care or nurse clinics affiliated with those departments.

5.3.2 Exclusion Criteria

- 1. Received peritoneal dialysis or chronic hemodialysis in the 3 months prior to index hepatitis B vaccination
- 2. Received all doses of their hepatitis B vaccine series in KPSC departments other than family practice or internal medicine or their affiliated departments as described above

5.4 Number of Subjects

HEPLISAV-B recipients: 25,000 patients

Other hepatitis B vaccine recipients: approximately 25,000 patients

The exact number of recipients will depend on the number of patients vaccinated with hepatitis B vaccine at the target and other medical centers during the study period.

6.0 STUDY METHODS

6.1 Exposure of Interest

The exposure of interest for this study is the index dose of hepatitis B vaccine (Section 4.2).

Hepatitis B vaccine exposure will be assigned at the cluster level. At target medical centers, providers in family practice and internal medicine departments will only be able to order HEPLISAV-B for hepatitis B vaccination of adult patients not on dialysis. Patients receiving an index dose of HEPLISAV-B in family practice or internal medicine departments will be included in the HEPLISAV-B cohort.

At non-target medical centers, providers in family practice or internal medicine departments will only be able to order a hepatitis B comparator vaccine other than HEPLISAV-B. Only patients receiving an index dose of comparator vaccine in family practice or internal medicine departments will be included in the comparator cohort. In recent years at KPSC, Engerix-B has been used for routine vaccination, while Recombivax-HB (Dialysis Formulation) has been used for dialysis patients. As dialysis patients are not included in this study, the comparator is expected to be Engerix-B.

Adults vaccinated with one or more doses of comparator hepatitis B vaccine prior to study initiation who did not complete the full 3-dose regimen may be given HEPLISAV-B if they

receive care at a HEPLISAV-B target medical center. These patients will be included in the primary analysis, while exploratory analyses will seek to identify differential outcomes between these patients and those who received their first dose of hepatitis B vaccine during the study period (Section 7.6).

While providers are advised to follow ACIP and RIPC recommendations, decisions regarding the appropriateness of administering a hepatitis B vaccination and the vaccination schedule will be determined by the healthcare providers and patients. Vaccine exposure will be identified retrospectively from the electronic health records, including vaccine, dose, manufacturer, and lot number entered at the time of vaccination. Data on vaccine exposure will be checked using quality control procedures described in Section 8.2 below.

6.2 Outcome of Interest

The outcome of interest is the first occurrence of AMI during the 13-month follow-up period for each patient.

6.2.1 Identification of Unconfirmed AMI

Hospitalizations with a diagnosis of AMI based on ICD-10-CM codes from databases of hospital discharge records and billing claims will be identified (Appendix 1). AMI cases will be extracted from any diagnosis position. The occurrence of AMI (ICD-10 I21.x) or subsequent AMI within 4 weeks of a previous AMI (ICD-10 I22.x) will be identified from inpatient encounters. ED encounters with these codes will be considered potential AMI if the patient was hospitalized or if the patient died the same or next day. The first AMI occurrence per individual within the study period will be considered a potential event. Historical AMI (ICD-10 I25.2) will not be considered a potential event.

Experienced staff members at KPSC will obtain relevant components from the electronic health record for potential AMI events. Information will be collected from 3 days prior to the potential AMI event date to 7 days following the potential AMI event date. Sections of the electronic health record to be collected if available will include:

- ED notes and orders
- Admission notes
- Transfer summary if seen at an outside facility
- Visit note associated with diagnosis date
- Consultant notes
- History and physical notes
- Laboratory results

Dynavax Technologies Corporation HEPLISAV-B[®]

- Cardiac procedures
- Imaging reports
- Discharge summary and final discharge note
- Death summary

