6.2.2 Adjudication

We will adjudicate potential AMI events identified from any diagnosis position using successfully implemented methods from previous studies: Cardiovascular Research Network (CVRN)^[26], Coronary Artery Risk Development in Young Adults (CARDIA)^[27], Cardiovascular Health Study (CHS)^[28], Atherosclerosis Risk in Communities (ARIC)^[29], and Women's Health Initiative^[30]. Abstracted information will be adjudicated independently by 2 trained cardiologist reviewers masked to vaccine exposure. Cases with disagreement will be reviewed by a third cardiologist. Adjudication will follow standardized criteria based on changes in troponin or other cardiac biomarker levels, cardiac signs and symptoms, clinical readings of the 12-lead ECGs, and imaging evidence, as outlined by the Third Universal Definition of Myocardial Infarction^[31]. All eligible hospitalized events will be classified as either definite, probable, unable to determine, or not AMI ^[29, 32]. Events will be considered "probable" if the available information from the medical record strongly suggests an AMI but some criteria required for a definite AMI are missing. Detailed adjudication criteria are provided in Appendix 1.

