6.2.3 Definition of primary AMI outcome

For the primary outcome, AMI will be defined as definite plus probable Type 1 AMI ^[31, 32]. A Type 1 AMI is due to a primary coronary event, such as plaque rupture, ulceration, fissuring, erosion, or dissection with resulting intraluminal thrombus in one or more of the coronary arteries leading to decreased myocardial blood flow or distal platelet emboli with ensuing myocyte necrosis. The patient may have underlying severe coronary artery disease (CAD) but on occasion non-obstructive or no CAD.

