7.3 Primary Analysis

For the final analysis of the primary objective, we will use a non-inferiority framework to test the null hypothesis of increased risk of Type 1 AMI among HEPLISAV-B recipients versus comparator vaccine recipients. Based on anticipated number of confirmed events, the study will have approximately 87% power to exclude a hazard ratio of 2.0 or greater (Section 7.9), testing the hypothesis: H_0 : $HR \ge 2$, H_a : HR < 2.

The rates of occurrence of first Type 1 AMI event during the study period among HEPLISAV-B recipients and comparator vaccine recipients will be compared using a Cox proportional hazards regression model employing inverse probability of treatment weighting (IPTW)^[33]. The IPTW provides an assessment of the closeness of match in the weighted analysis across all variables, providing a sense of the degree of control of imbalance between the vaccine exposure groups. Two tables will be created comparing the cohort of HEPLISAV-B recipients to the cohort of recipients of the comparator vaccine. The first table will be unweighted, showing the true distribution of recipient characteristics. The second table will be weighted by the inverse probability of treatment as estimated by a propensity score model. Standardized difference scores will be used to assess whether balance of covariates is achieved between the cohorts. These 2 tables will show the effectiveness of the weighting at reducing effective differences between the cohorts.

The primary analysis will be conducted on confirmed Type 1 AMIs. Variables to consider in the propensity model are listed in Section 6.3. The primary exposure will be vaccine group

(HEPLISAV-B vs. comparator vaccine), and the outcome will be confirmed AMI. Clustering by medical center will be considered through random effects variables representing medical center. Censoring events will include end of study, disenrollment from Kaiser Foundation Health Plan (allowing for a 31-day gap in membership), and death from causes other than AMI. A hazard ratio of AMI for HEPLISAV-B versus the comparator vaccine, adjusted for potential confounding factors, and associated 95% confidence interval will be reported.

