10.0 SIGNED AGREEMENT OF THE STUDY PROTOCOL

I have read the foregoing protocol, "Post-Marketing Observational Surveillance Study to Evaluate the Occurrence of Acute Myocardial Infarction," and agree to conduct the study according to the protocol and the applicable guidelines and regulations, and to inform all who assist me in the conduct of this study of their responsibilities and obligations.

Investigator's Signature

Date

Investigator's Name (Print)

APPENDIX 1: DEFINITIONS AND PROCEDURES FOR IDENTIFICATION AND ADJUDICATION OF ACUTE MYOCARDIAL INFARCTION

I. INTRODUCTION

This appendix defines terms and procedures for identification and adjudication of potential acute myocardial infarction (AMI). Section II lists the *International Classification of Diseases*, 10th *Revision, Clinical Modification* (ICD-10-CM) predefined codes for AMI events. Section III describes criteria based on the Third Universal Definition of Myocardial Infarction ^[31, 35]. Section IV lists steps for outcome classification ^[32]. Events will be independently adjudicated by two separate cardiologist reviewers, with a third cardiologist to review cases with disagreement. Cardiologist reviewers will be masked to the exposure.

II. ICD-10 Codes for Acute Myocardial Infarction

ICD-10 Code	Description
I21.0	ST elevation (STEMI) myocardial infarction of anterior wall
I21.01	ST elevation (STEMI) myocardial infarction involving left main coronary artery
I21.02	ST elevation (STEMI) myocardial infarction involving left anterior descending coronary artery
I21.09	ST elevation (STEMI) myocardial infarction involving other coronary artery of anterior wall
I21.1	ST elevation (STEMI) myocardial infarction of inferior wall
I21.11	ST elevation (STEMI) myocardial infarction involving right coronary artery
I21.19	ST elevation (STEMI) myocardial infarction involving other coronary artery of inferior wall
I21.2	ST elevation (STEMI) myocardial infarction of other sites
I21.21	ST elevation (STEMI) myocardial infarction involving left circumflex coronary artery
I21.29	ST elevation (STEMI) myocardial infarction involving other sites
I21.3	ST elevation (STEMI) myocardial infarction of unspecified site
I21.4	Non-ST elevation (NSTEMI) myocardial infarction
I21.9	Acute myocardial infarction, unspecified
I21.A	Other type of myocardial infarction
I21.A1	Myocardial infarction type 2
I21.A9	Other myocardial infarction type
I22.0	Subsequent ST elevation (STEMI) myocardial infarction of anterior wall

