AMI associated with stent restenosis defined as \geq 50% stenosis at coronary angiography or a complex lesion associated with a rise and/or fall of cTn values above the 99th percentile URL and no other significant obstructive CAD of greater severity following (a) initially successful stent deployment, or (2) dilation of a coronary artery stenosis with balloon angioplasty (<50%).

5. Type 5

Coronary artery bypass grafting (CABG) related AMI is arbitrarily defined by elevation of cardiac biomarker marker values (>10 x 99th percentile URL) in patients with normal baseline cTn (<99th percentile URL) AND at least 1 of the following:

- a. New pathological Q waves or new LBBB
- b. Angiographic findings consistent with a procedural complication
- c. Imaging evidence of new loss of viable myocardium or new regional wall motion abnormality

IV. OUTCOME CLASSIFICATION

An online event adjudication system will be created for the adjudicators to independently assess each of the criteria above. First, adjudicators will be asked if the event meets the criteria above. Second, adjudicators will be asked to consider all available information in the

health record to categorize the outcome. For this question, events are considered "definite AMI" if they meet the criteria described above. Events are considered "probable AMI" if the available information from the medical record strongly suggest an AMI but some criteria required for a definite AMI are missing. Third, adjudicators will classify definite and probable AMI by type.

- 1. Does this event meet the criteria above?
 - a. Yes
 - b. No
 - c. Unable to determine (specify reason)
- 2. Considering all available information in the health record, please categorize the outcome?
 - a. Definite AMI
 - b. Probable AMI (specify why not definite)
 - c. Not AMI
 - d. Unable to determine (if so indicate which criteria were unavailable)
- 3. If definite or probable AMI, indicate type.
 - a. AMI Type 1
 - b. AMI Type 2
 - c. AMI Type 3
 - d. AMI Type 4a
 - e. AMI Type 4b
 - f. AMI Type 4c
 - g. AMI Type 5

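### Section 6.2.1 picks each patient's first coded AMI as the potential event before its type is known, while Section 7.3 analyses the first Type 1 AMI, so some later Type 1 events have no stated route to adjudication.

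*Protocol*

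**What the plan says.** **Case finding (Section 6.2.1).** Hospitalizations with I21.x or I22.x codes are searched, and "AMI cases will be extracted from any diagnosis position". Emergency department encounters count if the patient was hospitalized or died the same or next day. The code list (Appendix 1, Table A-1) includes I21.A1, "Myocardial infarction type 2", and I21.A9, other types. One episode per patient is then selected: "The first AMI occurrence per individual within the study period will be considered a potential event". Records are collected for potential events, from 3 days before to 7 days after the event date.

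**Adjudication (Section 6.2.2 and Appendix 1, Section IV).** The material sent to the cardiologists is the set of potential events: "We will adjudicate potential AMI events identified from any diagnosis position". They first decide whether the event is an AMI, and then: "Third, adjudicators will classify definite and probable AMI by type".

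**Endpoint and analysis (Sections 6.2.3 and 7.3).** "For the primary outcome, AMI will be defined as definite plus probable Type 1 AMI". The comparison concerns "The rates of occurrence of first Type 1 AMI event during the study period". The listed censoring events are end of study, disenrollment and death from causes other than AMI. A first code that turns out not to be a Type 1 AMI is not among them.

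**The concern.** The first coded AMI and the first Type 1 AMI are different events. Section 6.2.1 fixes one episode per patient by code and date, before anyone knows whether it meets the endpoint. The screen is deliberately broad (any position, with Type 2 and other-type codes included), so some first hits will not qualify.

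Such a patient stays in the risk set under Section 7.3, but Section 6.2.1 names no route by which a later Type 1 AMI would be abstracted and adjudicated. Time at risk is counted while events in that time are not looked for. In a safety study whose aim is to exclude a doubling of risk, missed events cost power. If they were missed unequally between arms, they would also bias the hazard ratio.

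**Working it through.** **Step 1: follow one patient through the text.** Month 2: admission with I21.A1 in a secondary position. This is the first occurrence, so it is the potential event. It is adjudicated as Type 2, so it is not a primary outcome. Month 8: admission with a STEMI.

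| Section | What happens to the month-8 STEMI |
|---|---|
| 6.2.1 | Not the first occurrence, so not named as a potential event; outside the +7-day record window |
| 6.2.2 | Adjudication is of potential events, so no stated route |
| 6.2.3, 7.3 | If confirmed, it is the first Type 1 AMI and should count |
| 7.3 censoring | Patient still at risk at month 8 |

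The same holds if the month-2 code is judged not AMI or undeterminable.

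**Step 2: reproduce the plan's figures (Section 7.9, Table 7-1).**
- Events: 50,000 × 1.02 person-years × 1.5/1000 = 76.5, against 78 stated.
- Power to exclude a hazard ratio (HR) of 2.0 when the true HR is 1, 1:1 allocation, one-sided 0.025: Φ(ln 2 × √D / 2 − 1.96). At D = 78 this is Φ(3.061 − 1.960) = 0.8645, against 0.865 stated.

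**Step 3: size of the loss.** The protocol does not say how often a Type 1 AMI follows a non-qualifying first code. All three inputs here are assumptions: 100 to 150 patients with any coded AMI; 30 to 50% of first hits not confirmed as Type 1; 3 to 10% of those with a later Type 1 AMI in follow-up. The 78 planned events are taken to include the ones that would be missed.
- Low: 100 × 0.30 × 0.03 = 0.9 events (1.2% of 78).
- High: 150 × 0.50 × 0.10 = 7.5 events (9.6% of 78).

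| Events left | Power |
|---|---|
| 78 | 86.5% |
| 77.2 (1% lost) | 86.1% |
| 74 | about 84.6% |
| 71 | 83.1% |
| 70.2 (10% lost) | 82.7% |

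**Step 4: vary the inputs.**
- *Anchored to Table 4-1.* It shows 126 hospitalized AMIs in 93,730 recipients over 12 months. Scaled: 126 / 93,730 × 50,000 = 67, and × 13/12 = 73 over 13 months. With the same percentages, 73 × 0.30 × 0.03 = 0.7 and 73 × 0.50 × 0.10 = 3.7 events are lost; power is 86.2% and 84.8%. The table does not state the diagnosis position, so an any-position count could be higher.
- *Rate-based.* Assume K patients with a non-qualifying first code, a later Type 1 rate h, and 0.51 years of remaining follow-up (half of 1.02). Missed events = K × (1 − exp(−0.51h)). K = 39 and h = 15/1000 gives 0.3 events (power 86.3%). K = 234 and h = 100/1000 gives 11.6 events (power 80.6%). The upper corner needs three times as many non-qualifying patients as planned events, together with a very high rate.

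**Step 5: effect on the hazard ratio.** If fractions a (HEPLISAV-B) and b (comparator) of events are missed, observed HR ≈ true HR × (1 − a)/(1 − b).
- a = b = 5%: 2.0 stays 2.0.
- a = 5%, b = 0: 2.0 × 0.95 = 1.90. With a = 10%, b = 0: 1.80.
- a = 0, b = 5%: 2.0 / 0.95 = 2.11, the opposite direction.

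The protocol has no figure for a or b, so these are illustrations only.

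**The case against.** **The text does not say that later episodes are discarded.** This is correct. Section 6.2.1 contains no word such as only, and its sentence could be meant as a rule to count one event per person. A reader might infer that the protocol forbids adjudication of any later episode, so that such events can never enter the analysis. That goes beyond the wording. What stands is that naming the first occurrence per individual has no other evident purpose, and no section sends a later episode to adjudication.

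**Other wording points the other way.** Section 7.3 would count the later Type 1 AMI, and Section 6.2.2 says "All eligible hospitalized events will be classified as either definite, probable, unable to determine, or not AMI". But Section 6.2.2 does not define eligibility apart from the potential events of Section 6.2.1, and Section 7.3 states the endpoint without supplying the case finding. This shows that the sections conflict; it does not resolve the conflict.

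**The record window reaches 7 days forward.** A Type 1 AMI within a week of the first code may appear in the same records. This limits the gap to later events.

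**The step belongs in a statistical analysis plan or adjudication charter.** A missing detail would. Here the protocol states a selection rule that does not match its own endpoint, and an analysis plan cannot analyse episodes that were never abstracted.

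**The loss is small, and the study can be extended.** This is largely right. Section 6.5 allows a longer vaccination period if event rates run low, and most of the assumed inputs cost under 4 points of power. Extension does not repair incomplete ascertainment, however.

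**Bias between arms.** A reader might infer that the rule favours non-inferiority because arms are defined by medical center. The protocol does not support this. Section 6.4 says that the share of events derived from claims may differ between centers, and Section 8.1 reports cases lacking data as undeterminable, so an unequal loss is possible. Nothing shows that it occurs or in which direction, and the adjudicators are masked.

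**Conclusion.** The point holds as a conflict between a stated case-finding rule and the stated endpoint. Followed literally, Section 6.2.1 leaves a Type 1 AMI unascertained if it comes more than about 7 days after a non-qualifying first code, while Section 7.3 keeps the patient at risk for exactly that event.

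The size is modest and rests wholly on assumptions: about 1 to 7 of 78 events, with power of about 83-86% instead of 86.5%. Anchoring to Table 4-1 puts it at the lower end; only extreme inputs take it below 82%. The plan's own event and power figures reproduce and are not in dispute. The hazard ratio is biased only if the proportional loss differs between arms, which the documents do not show. The reason to act is complete ascertainment of the primary safety endpoint at very low cost, more than the loss of power.

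**What to change.** Reconcile Section 6.2.1 with Section 7.3 by replacing the sentence on the first occurrence with a rule of this kind: every distinct hospitalization with an I21 or I22 code during the 13-month follow-up, or emergency department encounter with such a code that meets the existing death criterion, is a potential event; each patient's potential events are adjudicated in date order until the first definite or probable Type 1 AMI, and the date of that event is the primary event date. Collect the −3 to +7 day records around each episode adjudicated.

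The cost is one sentence and a few extra charts for the existing masked cardiologists and online system. On the assumptions above, 100 × 0.30 = 30 to 150 × 0.50 = 75 patients would have a non-qualifying first code, and only those with a later coded episode add work. No stated sample size, event target or power figure changes.
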